#### Study Population

Twenty-four Paroxysmal Atrial-Fibrillation (PAF) patients, amenable to catheter-based AF ablation therapy comprising of Pulmonary Veins Isolation (PVI). We suggest that 4 will patients decline to participate. The overall number of patients in the study is twenty.

#### Key Inclusion Criteria

1. Male or female patients, age  $\geq$  18 and  $\leq$  80 years.
2. Paroxysmal atrial fibrillation (PAF)

3. Able to provide written informed consent form to participate in the study, prior to any study related procedures.
4. Able and willing to comply with the study protocol requirements.
5. A female subject is eligible if not of child bearing potential or has a negative pregnancy test within the previous 7 days.

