#### Study Design

Prospective, single-center, non-randomized, non-blinded, open label, and single arm study.

All procedures will be performed under CARTO 3 guidance for the treatment of atrial fibrillation (AF). The EPD D700 system will be used interchangeably, to record pre-, during and immediate post-ablation tissue characteristics and compute likelihood of lesion transmurality and permanency. Additionally, D700 system safety, feasibility, usability and clinical applicability will be documented.

The entire procedure will be conducted as customary, using standard and approved off-the-shelf equipment (body surface electrodes, diagnostic and irrigated ablation catheters, RF generator and recording system), in a completely clinically independent manner from the EPD D700 system. The physician will neither use nor rely on any of the D700 system output for clinical decision making and will be blinded to the D700 lesion assessment forecasts. One month following the initial procedure, a repeated procedure will be performed for gap detection and its results will be correlated with the D700 predictions.

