## Baseline Assessment

- Eligibility according to inclusion and exclusion criteria.
- Obtaining signed informed Consent Form (ICF).
- Demographics.
- Medical history.
- Concomitant medications.
- Disease oriented physical examination including vital signs.
- 12 lead ECG.
- Standard laboratory tests;
  - Complete blood count
  - Coagulation studies if appropriate
  - Serum creatinine and electrolytes
  - Liver function tests
  - CRP
- TTE or TEE.
- Pregnancy test, if applicable.

MASTER

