## Study procedures

- **Cardiac CT (pre-procedure imaging) or MR.**
- **CT/MR post-processing and analysis at EPD Research (Caesarea, Israel):**
  - **Cardiac chambers' segmentation**
  - **Electrical fields computation**
  - **Optional recommended PVI ablation lines**
  - **Optional preliminary lesion forecast at the point level**
- **Forwarding the ready to use pre-planned data to the site.**
- **First AF ablation procedure (Figure 1):**
  - EPD D700 system installed in the EP cath-lab.
  - Deployment of body surface electrodes (patches) by the local EP technician/nurse under supervision of EPD Research team members, to be used later by both the CARTO3 and EPD D700 system, interchangeably, according to the diagrams in Appendix 1.
  - Deployment of BWI body surface magnetic sensors according to the customary setup guidelines.
  - Connecting the ThermoCool SmartTouch ablation catheter via the commercially available extension cables to the CARTO3 system according to the diagrams in Appendix 1.
  - Connecting the Stockert RF ablation generator to the CARTO3 system according to the diagrams in Appendix 1.
  - Registration of the pre-acquired 3D CT or MR images of the Right Atrium (RA) with EPD D700, using CARTOMERGE module.
  - Registration of the pre-acquired 3D CT or MR images of the RA with EPD D700 system under fluoroscopy and or CARTO3-guidance.
  - Performance of Transseptal Procedure under fluoroscopy and/or ultrasound (TEE or ICE) guidance.
  - Registration of the pre-acquired 3D CT or MR images of the Left Atrium (LA) and Pulmonary Veins (PVs) with CARTO3 using CARTOMERGE module.
  - Registration of the pre-acquired 3D CT or MR images of the LA and PVs with EPD D700 system under fluoroscopy or CARTO3-guidance.
  - Targeted navigation inside the LA and reaching the 1st, either user-determined or computer recommended, point of the 1st preplanned PVI ablation lines.
  - Performing the specific ablation strategy while ascertaining contiguity using VisiTAG module, i.e. 5-6 mm between consecutive ablation points, and moving along the PVI line systematically in preplanned continuous order. The specific ablation parameters to be used, i.e. 30 W 30 and 25W a30 sec in anterior and posterior LA wall, respectively; as well as the desired Ablation Index to be reached, will be determined solely by the operator regardless of the system's recommendation.

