### DURABLE - 1st Procedure

[figure not shown]

Figure 1: Step-by-step 1st procedure, using both CARTO3 and D700 interchangeably.

■ **Second AF ablation procedure (Figure 2):**

- The second procedure will be conducted 1 month after the initial procedure in a similar set up under CARTO3 guidance.
- After repeated registration, with the previous pre-acquired 3D image, the LA will be remapped.
- In order to functionally identify existing gaps, remaining gaps will be sought for by electrical functional test.

MASTER

- If such gaps will be encountered, the physician will apply the customary touch-up approach.
- The location of gaps around the PVs will be reported in 8-16 segments (Figure 3).

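### The 7-day pregnancy-test window has no anchoring event, and no repeat check is listed before the study-mandated second procedure at one month.

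*Combined protocol and SAP*

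**What the plan says.** All references are to the combined protocol and SAP.

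- **Key Inclusion Criteria, item 5:** "A female subject is eligible if not of child bearing potential or has a negative pregnancy test within the previous 7 days". No event is named from which the 7 days are counted. Women are admitted from age 18.
- **Key Exclusion Criteria:** pregnancy is not listed, so item 5 is the only pregnancy safeguard in the document.
- **Baseline Assessment:** this section lists "Eligibility according to inclusion and exclusion criteria" and "Pregnancy test, if applicable". Neither appears again later.
- **Study procedures:** the sequence opens with "Cardiac CT (pre-procedure imaging) or MR", followed by off-site processing and then "Forwarding the ready to use pre-planned data to the site". All of this precedes the first procedure, and no duration is given. Fluoroscopy is one of the permitted means of guiding registration and transseptal access.
- **Study Design:** "One month following the initial procedure, a repeated procedure will be performed for gap detection".
- **Second AF ablation procedure:** "The second procedure will be conducted 1 month after the initial procedure in a similar set up under CARTO3 guidance". The listed steps begin with "After repeated registration, with the previous pre-acquired 3D image, the LA will be remapped", then a functional test for gaps, touch-up where needed, and reporting of gap locations. No pregnancy test or eligibility re-check is among them.
- **Data to be collected during the procedures:** fluoroscopy time is recorded under this plural heading.

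**The concern.** A pregnancy test speaks only for the time at which it is taken, which is why the sponsor limited its age to 7 days. The criterion is nevertheless checked once, and the study then schedules a second invasive procedure a month later. That procedure serves the gap map, and the text does not make it conditional on symptoms or recurrence. A woman of child-bearing potential could enter it, with possible fluoroscopy, on a test taken before the first procedure.

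The missing anchor is a separate weakness. Consent, enrolment, pre-procedure imaging and the first procedure are all plausible reference events. Two sites staff could apply item 5 differently and both be compliant, and a monitor could not verify it.

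What is at stake is participant safety and a criterion that can be applied. The statistical analysis is affected only through an occasional missing month-1 map.

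**Working it through.** The plan states no figure to reproduce, so the check is date arithmetic.

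**Inputs**
- w, days from the test to the event that anchors the window: 0 to 7 (Key Inclusion Criteria, item 5).
- m, days from the first to the second procedure: the plan says one month and gives no visit window. Taken as 28 to 31 (assumption).
- g, days from the anchoring event to the first procedure: not stated.

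**Formula:** age of the test at the second procedure = w + g + m.

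**Reading A: the window counts back from the first procedure (g = 0, assumption)**
- m = 28: 0 + 28 = 28 to 7 + 28 = 35 days, or 4.0 to 5.0 weeks.
- m = 31: 0 + 31 = 31 to 7 + 31 = 38 days, or 4.4 to 5.4 weeks.
- Overall: 28 to 38 days.

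**Reading B: the window counts back from consent or enrolment (g > 0)**

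Imaging, off-site processing and return of the data all come before the first procedure, so some gap is plausible. The plan does not give its length. The values of g below are illustrative assumptions.

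| g (days) | Lowest: 0 + g + 28 | Highest: 7 + g + 31 | Weeks |
|---|---|---|---|
| 7 | 35 | 45 | 5.0 to 6.4 |
| 14 | 42 | 52 | 6.0 to 7.4 |
| 28 | 56 | 66 | 8.0 to 9.4 |

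The text sets no upper limit on g, so Reading A is the low end. On either reading, a test taken before the first procedure is at least 28 days old at the second.

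**With the 7-day criterion applied again before the second procedure:** the test is at most 7 days old at that point.

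**The case against.** The strongest reply is that item 5 is an entry criterion. It decides who may join, eligibility is checked at baseline, and nothing applies the 7 days to a later procedure. That is correct. A reader might infer that the second procedure breaches the protocol's limit by a factor of 38/7 = 5.4 at worst. The documents do not support this, because no limit is set for that procedure.

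Other objections stand in part:

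- **Silence is weak evidence.** The procedure lists are mostly technical, and no clinical work-up is repeated for the first procedure either. The criteria are headed as key ones, and site routine may include a test. A reader might infer that no test will be done; the documents show only that none is required. For a repeat procedure done for the study, the protocol should state the requirement.
- **Radiation exposure is not certain.** A reader might count three radiation steps: CT, first procedure and second procedure. That is a maximum. Imaging may be MR, fluoroscopy is optional at several steps, and the second procedure reuses the earlier image. With no turnaround time given, CT and the first procedure could also fall within one 7-day window.
- **Pregnancy is not the only condition that can newly arise in a month.** Active coronary ischemia, infarction or stroke, cardiac thrombus and severe renal insufficiency (exclusion items 4, 5, 7 and 9) can too, and none is listed for re-checking. Pregnancy is distinctive here in that the sponsor attached an explicit time limit to its test.
- **Few women may be affected.** Among 20 patients aged 18 to 80 the number is unknown and could be zero. This bears on the size of the problem. The wording of the criterion is unclear either way.

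**Conclusion.** The point holds as a gap in the safeguard. Item 5 names no anchoring event, the test and the eligibility check are listed only at baseline, and the study-mandated procedure at one month carries no listed re-check. The baseline test is 28 to 38 days old by then if the window is anchored to the first procedure and a month is 28 to 31 days. It is older if the anchor is earlier.

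The conclusion rests on those two assumptions and on the absence of a re-check from the text. It does not show that a limit is breached, that fluoroscopy will be used in every case, or that sites will omit testing. The change is worth making because it is cheap and concerns participant safety.

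**What to change.** Reconcile item 5 of the Key Inclusion Criteria, the Baseline Assessment and the steps of the second procedure:

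1. Name in item 5 the event from which the 7 days are counted.
2. Apply the sponsor's own 7-day test criterion again before the second procedure, for the same women to whom item 5 applies, and list the check among that procedure's steps.
3. Have the sponsor and investigator state how a positive result is handled, and how a missing month-1 gap map is then reported. The handling itself is a clinical decision and is left to them.

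The cost is a short amendment, one extra pregnancy test in what may be only a few women, and an occasional participant without a month-1 map. In a study of 20 each lost map is 1/20 = 5% of participants, so the reporting rule should be written in advance.

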## Key Exclusion Criteria

1. Any planned surgical or endovascular intervention within 30 days before or after the index procedures.
2. Subject is enrolled in another drug or device study protocol that has not reached its primary endpoint.
3. Previous AF ablation therapy.
4. Clinical evidence of active coronary ischemia, significant Valvular heart disease, or hemodynamically significant congenital cardiac abnormality.
5. Patient had experienced myocardial infarction (MI), stroke (CVA) or transient ischemic attack (TIA) or other neurological disturbances.
6. Patient has a pacemaker.
7. Thrombi detected in the heart.
8. Life expectancy less than 12 months.
9. Known severe renal insufficiency.
10. Known allergy to Iodine.

## Baseline Assessment

- Eligibility according to inclusion and exclusion criteria.
- Obtaining signed informed Consent Form (ICF).
- Demographics.
- Medical history.
- Concomitant medications.
- Disease oriented physical examination including vital signs.
- 12 lead ECG.
- Standard laboratory tests;
  - Complete blood count
  - Coagulation studies if appropriate
  - Serum creatinine and electrolytes
  - Liver function tests
  - CRP
- TTE or TEE.
- Pregnancy test, if applicable.

MASTER

## Study procedures

- **Cardiac CT (pre-procedure imaging) or MR.**
- **CT/MR post-processing and analysis at EPD Research (Caesarea, Israel):**
  - **Cardiac chambers' segmentation**
  - **Electrical fields computation**
  - **Optional recommended PVI ablation lines**
  - **Optional preliminary lesion forecast at the point level**
- **Forwarding the ready to use pre-planned data to the site.**
- **First AF ablation procedure (Figure 1):**
  - EPD D700 system installed in the EP cath-lab.
  - Deployment of body surface electrodes (patches) by the local EP technician/nurse under supervision of EPD Research team members, to be used later by both the CARTO3 and EPD D700 system, interchangeably, according to the diagrams in Appendix 1.
  - Deployment of BWI body surface magnetic sensors according to the customary setup guidelines.
  - Connecting the ThermoCool SmartTouch ablation catheter via the commercially available extension cables to the CARTO3 system according to the diagrams in Appendix 1.
  - Connecting the Stockert RF ablation generator to the CARTO3 system according to the diagrams in Appendix 1.
  - Registration of the pre-acquired 3D CT or MR images of the Right Atrium (RA) with EPD D700, using CARTOMERGE module.
  - Registration of the pre-acquired 3D CT or MR images of the RA with EPD D700 system under fluoroscopy and or CARTO3-guidance.
  - Performance of Transseptal Procedure under fluoroscopy and/or ultrasound (TEE or ICE) guidance.
  - Registration of the pre-acquired 3D CT or MR images of the Left Atrium (LA) and Pulmonary Veins (PVs) with CARTO3 using CARTOMERGE module.
  - Registration of the pre-acquired 3D CT or MR images of the LA and PVs with EPD D700 system under fluoroscopy or CARTO3-guidance.
  - Targeted navigation inside the LA and reaching the 1st, either user-determined or computer recommended, point of the 1st preplanned PVI ablation lines.
  - Performing the specific ablation strategy while ascertaining contiguity using VisiTAG module, i.e. 5-6 mm between consecutive ablation points, and moving along the PVI line systematically in preplanned continuous order. The specific ablation parameters to be used, i.e. 30 W 30 and 25W a30 sec in anterior and posterior LA wall, respectively; as well as the desired Ablation Index to be reached, will be determined solely by the operator regardless of the system's recommendation.

- Before, during and immediately after each ablation point, the EPD D700 system will record (for a few seconds) specific dielectric characteristics from the catheter tip. These readings, reflecting estimated transmurality and probability of the lesion's permanency, will be analyzed in the post-procedure phase and will not be considered by the user during the procedure.
- Thirty minutes after the completion of the full ablation plan, a formal acute electrical isolation test will be performed to identify remaining gaps.
- IV Adenosine infusion, a bolus of 12-18mg, will be performed to identify additional existing dormant conduction.
- Touch-up ablations will be added according to the two previous tests' findings.
- The procedure will be concluded only after the physician has decided there are currently no remaining identifiable gaps and the PVI is, based on current knowledge, deemed durable.

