## DURABLE-I STUDY:

### DIELECTRIC UNRAVELLING OF RADIOFREQUENCY ABLATION EFFECTIVENESS

#### Study Purpose

The purpose of this study is to evaluate real-time gap detection using EPD D700 dielectric sensing compared with customary electrical isolation tests and Adenosine infusion at the end of the procedure. Furthermore, safety, usability and clinical applicability of the system for guided AF ablation will be confirmed.

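### No visible text requires the D700 predictions to be final, or those who produce them to be masked, before the 1-month remap with which they are correlated

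*Combined protocol and SAP*

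**What the plan says.** All references are to the combined protocol and SAP.

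- **Aim.** Study Purpose is to "evaluate real-time gap detection using EPD D700 dielectric sensing compared with customary electrical isolation tests and Adenosine infusion".
- **Prediction and reference.** In Study Design the D700 is to record tissue characteristics around each ablation and "compute likelihood of lesion transmurality and permanency". A second procedure one month later looks for gaps, and "its results will be correlated with the D700 predictions".
- **Timing.** Under Study procedures (first procedure), the readings "will be analyzed in the post-procedure phase and will not be considered by the user during the procedure". No date or event closes that phase. The only forecast clearly placed before the first procedure is listed as "Optional preliminary lesion forecast at the point level".
- **Masking.** Study Design says the physician "will be blinded to the D700 lesion assessment forecasts". The study as a whole is labelled "Prospective, single-center, non-randomized, non-blinded, open label, and single arm study". Nothing is said about who analyses the readings, or whether they may see the remap findings.
- **Units.** Readings are taken at each ablation point, with points 5–6 mm apart. Gaps at the second procedure are reported in 8 to 16 segments. No rule turns point readings into a segment prediction, and no cut-off or algorithm version is given.
- **Touch-ups.** In the first procedure the isolation test and adenosine come after the planned ablation, and touch-up lesions follow from their findings.

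**The concern.** A study that compares a predictor with a reference standard can need masking in two directions. Keeping the D700 output from the physician stops the predictor from influencing treatment, and the plan does this. Keeping the remap results from those who produce the predictions stops the reference from influencing the predictor, and no visible text does this.

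Recording the raw readings early does not settle the matter. The score, any cut-off, the segment resolution and the rule for combining points into a segment all lie between a reading and a prediction. If any of them is chosen with the gaps known, agreement is measured on the data used to choose it and is biased upwards. No separate validation set is described. Patients undergo a second procedure that supplies the reference for the durability question, so the comparison should be a genuine test of prediction.

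The touch-ups raise a smaller, related matter. Readings from touch-up lesions are taken after the isolation test and adenosine, so they cannot count as calls made before those tests. They do belong in the comparison with the remap. The plan does not say which readings enter which comparison.

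**Working it through.** **1. The text.** Three statements decide the point: the analysis falls in a phase with no stated end, the remap is the reference, and the physician is the only person masked. No other visible section gives a lock, freeze, time stamp, algorithm version, cut-off or analyst masking.

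**2. The plan's own figures.** Study Population gives 24 patients less 4 expected to decline: 24 − 4 = 20, as stated. With 8 to 16 segments each, the units are 20 × 8 = 160 to 20 × 16 = 320. The documents give no power calculation, gap rate or performance target to reproduce.

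**3. Illustration of size.** Let J(c) = sensitivity(c) + specificity(c) − 1 at cut-off c. For a worthless score the true J is 0 at every c. If c is chosen after the gaps are known, the reported value is the maximum of J(c) over c on the same data, which is positive on average. The assumptions, none of them from the documents, are:

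- gap rates of 5%, 10% and 20%;
- independent segments;
- a worthless score whose direction is fixed in advance;
- for the last two columns, a choice of the best of three readings with correlation 0.7.

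The values are means over 2,000 simulated trials per row.

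| Segments | Gap rate | Expected gaps | Mean J, cut-off chosen afterwards | Mean J, best of three as well | Mean AUC, best of three |
|---|---|---|---|---|---|
| 160 | 5% | 8 | 0.218 | 0.285 | 0.554 |
| 160 | 10% | 16 | 0.155 | 0.205 | 0.537 |
| 160 | 20% | 32 | 0.119 | 0.156 | 0.530 |
| 320 | 5% | 16 | 0.152 | 0.201 | 0.534 |
| 320 | 10% | 32 | 0.111 | 0.146 | 0.526 |
| 320 | 20% | 64 | 0.083 | 0.109 | 0.519 |

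With one reading the mean AUC is 0.50 in every row, because AUC does not use a cut-off.

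**4. Check by hand.** For a worthless score the maximum of J is the one-sided two-sample Kolmogorov–Smirnov statistic. With m gaps and k intact segments its large-sample mean is √(π/8) × √(1/m + 1/k), where √(π/8) = 0.627.

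- 160 segments, 5%: m = 8, k = 152, so 0.627 × √(0.1250 + 0.0066) = 0.627 × 0.363 = 0.23 (simulated 0.218).
- 320 segments, 20%: m = 64, k = 256, so 0.627 × √(0.0156 + 0.0039) = 0.627 × 0.140 = 0.09 (simulated 0.083).

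The formula slightly exceeds the simulation, but the size agrees. The bias is largest where gaps are few.

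**5. Clustering.** With a within-patient correlation of 0.2 in both gaps and readings, the range in the fourth column becomes about 0.09–0.24. The effect does not depend on treating segments as independent.

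**The case against.** The strongest reply is that the documents already point to predictions made before the remap. Study Design speaks of forecasts and predictions, and masking the physician to forecasts presupposes that they exist. The data list includes a lesion assessment at each ablation point. The statement about later analysis sits in the description of the first procedure, so its ordinary meaning is after that procedure. Figures 1 and 2 are not shown and could carry a timing step. All of this stands. It makes the point an unstated safeguard and not a demonstrated flaw, but none of it makes the order a requirement.

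The reply on size also stands in part. The plan says only that results will be correlated and names no cut-off, index or test. The inflation in J needs a dichotomised analysis. With one fixed score, a threshold-free measure such as AUC is unaffected by a later choice of cut-off. It is affected only if the score itself is also selected, and then by a few hundredths in this illustration.

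A reader might infer three stronger things that the documents do not support:

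- **That tuning after the remap is planned.** No text says so.
- **That EPD staff attend the remap and see the gaps.** At the first procedure, patches are placed "under supervision of EPD Research team members", and the second procedure has a similar arrangement. But the description of the second procedure names no EPD staff and no D700 step, so their attendance is conjecture.
- **That the non-blinded label means the analysts are unmasked.** In a single-arm study that label describes the treatment and says nothing about analysts' access to results.

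On touch-ups, the order of steps already separates the readings in time, and the exported point list and tags probably allow the split. Only a stated rule is missing.

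**Conclusion.** The point holds as a cheap improvement, with medium confidence. The visible plan neither requires the D700 predictions to be final before the 1-month remap nor keeps those who produce them from its results. That leaves open a route to overstated agreement in a key comparison; it does not show that the route will be taken.

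The size is illustrative. For a worthless score, a cut-off chosen afterwards gives a mean sensitivity + specificity − 1 of about 0.08–0.22 in place of 0, and leaves AUC at 0.50. Choosing the best of three correlated readings as well gives AUC of about 0.52–0.55. These figures rest on assumed gap rates of 5–20%, independent segments and, for the first, a dichotomised analysis. The textual conclusion does not depend on them.

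**What to change.** In Study Design and in the first-procedure part of Study procedures, state that:

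1. Each patient's D700 predictions come from a named algorithm version and are stored time-stamped and read-only before that patient's second procedure.
2. Those who produce the predictions are masked to remap results until that lock.
3. Any cut-off, the segment resolution and the point-to-segment rule used in the main analysis are fixed before predictions are linked to remap results.
4. Later re-tuning is allowed but labelled exploratory, with leave-one-patient-out validation.
5. Touch-up readings are flagged in the export. The comparison with the isolation test and adenosine uses only readings made before those tests; the 1-month comparison uses all first-procedure readings.

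Item 3 asks for less than fixing every choice before the first remap. If the main analysis uses a threshold-free measure, no cut-off is needed.

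The cost is protocol text in two places, one flagged export per patient and masking of the D700 analysts. No patients or procedures are added. The real downside is that one version of the algorithm must be frozen, and the reported performance may be less favourable.
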